### **Exclusion Criteria:**

1. Previous treatment of target lesion with a stent, angioplasty, or other mechanical device, or plan to perform one of these procedures
2. Plan to perform concomitant angioplasty or stenting of an extracranial vessel tandem to an intracranial stenosis
3. Intracranial tumor (except meningioma) or any intracranial vascular malformation
4. Thrombolytic therapy within 72 hours prior to enrollment
5. Progressive neurological signs within 24 hours prior to enrollment
6. Any intracranial hemorrhage (parenchmal, subarachnoid, subdural, epidural) within 90 days
7. Any untreated chronic subdural hematoma

8. Intracranial arterial stenosis due to arterial dissection, Moya Moya disease; any known vasculitic disease; herpes zoster, varicella zoster or other viral vasculopathy; neurosyphilis; any other intracranial infection; any intracranial stenosis associated with CSF pleocytosis; radiation induced vasculopathy; fibromuscular dysplasia; sickle cell disease; neurofibromatosis; benign angiopathy of central nervous system; post-partum angiopathy; suspected vasospastic process, suspected recanalized embolus
9. Presence of any of the following unequivocal cardiac sources of embolism: chronic or paroxysmal atrial fibrillation, mitral stenosis, mechanical valve, endocarditis, intracardiac clot or vegetation, myocardial infarction within three months, dilated cardiomyopathy, left atrial spontaneous echo contrast, ejection fraction less than 30%
10. History of upper extremity ischemia, known subclavian or brachial artery stenosis, subclavian steal syndrome, any upper extremity soft tissue, orthopedic or vascular injury, or mastectomy or other procedure that may contraindicate taking blood pressure or having a cuff on the arm for the conditioning treatment
11. Difference in systolic blood pressure of > 15 mm Hg between both arms
12. Known allergy or contraindication to aspirin or clopidogrel
13. Active peptic ulcer disease, major systemic hemorrhage within 30 days, active bleeding diathesis, platelets < 100,000, hematocrit < 30, INR > 1.5, clotting factor abnormality that increases the risk of bleeding, current alcohol or substance abuse, uncontrolled severe hypertension (systolic pressure > 180 mm Hg or diastolic pressure > 115 mm Hg), severe liver impairment (AST or ALT > 3 x normal, cirrhosis), subject on dialysis
14. Major surgery (including open femoral, aortic, or carotid surgery, cardiac) within previous 30 days or planned in the next 30 days after enrollment
15. Indication for warfarin or heparin beyond enrollment (**NOTE: exceptions allowed for subcutaneous heparin for deep vein thrombosis (DVT) prophylaxis while hospitalized**)
16. Diabetic subjects taking sulfonylurea drugs
17. Severe neurological deficit that renders the subject incapable of living independently
18. Dementia or psychiatric problem that prevents the subject from following the protocol reliably
19. Co-morbid conditions that may limit survival to less than 3 months
20. Pregnancy or of childbearing potential and unwilling to use contraception for the duration of this study
21. Claustrophobia requiring sedation for MRI or any metallic implants or MRI incompatible devices that do not permit the patient to have an MRI
22. Enrollment in another study that would conflict with the current study

## 5. SCREENING, INFORMED CONSENT, RANDOMIZATION AND ENROLLMENT OF SUBJECTS

Subjects will be screened from the inpatient and outpatient stroke service at all four participating sites. All eligibility criteria are determined by evaluations performed as routine standard of care. The principles of Informed Consent, according to FDA Regulations and ICH guidelines on GCP, will be followed. Each Investigator will submit a copy of the proposed consent form, together with the study protocol, to the appropriate IRB for approval. All subjects must provide informed consent to participate and only the participant can provide informed consent, which must be cosigned by a study investigator. Once a subject's eligibility has been confirmed by the site investigators, the subject will be approached to participate in the trial. The consent form includes a section describing a screening process whereby the subject will have a test RLIC treatment with the Doctormate device (Figure 2) with inflation of the blood pressure cuffs on both arms simultaneously to a SBP of 200 mmHg for 5 minutes to ensure that the subject can tolerate the treatment. Subjects who cannot tolerate the treatment will be called by the study coordinator at 1 week but will not participate further in the trial. If the subject can tolerate the screening treatment and wishes to participate in the trial, the coordinator will email the study statistician at MUSC who will provide the randomized treatment assignment by email.

Moreover, in terms of acute cardioprotection, pre-clinical studies have shown that 4 to 6 cycles of 5-minute durations appear optimal. Using 4 cycles instead of 5 cycles (the regimen used in the Chinese trials) will lessen the total duration of each treatment from 45 minutes to 35 minutes, which we expect will increase adherence. We chose to measure changes in CBF and biomarkers at 30 days for this pilot study because some preliminary human studies by the MCG group show that CBF increases within 6-24 hours of first use of RLIC, and a preclinical study (in a mouse model) shows that the increased CBF after RLIC is sustained to 28 days with daily RLIC treatment. Moreover, the first 30 days after enrollment in SAMMPRIS was the highest risk period for recurrent stroke so it is important to determine if the CBF and biomarker responses to RLIC persist for this period.

## 7. AGGRESSIVE MEDICAL MANAGEMENT

The medical management for all subjects enrolled in this pilot study will consist of the current standard of care recommended by the American Heart Association and American Stroke Association for patients with ICAS established by the SAMMPRIS trial. This consists of dual antiplatelet therapy (aspirin 325 mg per day, clopidogrel 75 mg per day) and intensive risk factor management targeting a systolic blood pressure < 140 mm HG, an LDL cholesterol < 70 mg /dl, non-HDL cholesterol < 100mg/dl, smoking cessation, and hemoglobin A1c < 7% in diabetics.

## 8. BLOOD BIOMARKER MEASUREMENTS

The blood biomarkers that will be measured are putative biomarkers of RLIC and known inflammatory and fibrinolytic markers associated with the development or progression of ICAS, or increased risk of stroke in patients with ICAS. These consist of: Nitrite, IL-10, SDF1, Micro RNA 144, Lp-PLA2, IL-6, hsCRP, Soluble E-selectin, ICAM, MMP-9, PAI-1, tPA, and ADMA. We will measure the blood biomarkers at baseline and close-out (33-35 days after enrollment) in all 10 subjects. All blood biomarkers will be mailed to the Blood Biomarker Core at MCG where the levels of biomarkers will be measured blinded to site, subject, treatment assignment and time point.

**Figure 2.** The RLIC device used in the Chinese trials will be used in this pilot study and is shown being applied to [name], a Co-PI of this pilot study at Georgia Regents University (center)

## **9. MRI MEASUREMENTS OF CBF AND OTHER PERfusion PARAMETERS**

ASL MRI will be used to provide quantitative measurements of CBF in all 10 subjects in the study (at baseline and at close-out). ASL does not require the injection of contrast material and can be repeated over time without risk to patients. **We will use a standardized ASL protocol agreed upon by the study radiologists and physicists at the 4 participating sites that can be applied to different MRI scanner platforms.** Each subject will undergo all MR studies for this pilot on the same scanner to limit slight variations in images from scanner to scanner. We have already tested the feasibility of using our planned ASL MRI protocol under a MCG / UCLA IRB-approved protocol. Six subjects with recent stroke from ICAS underwent ASL MRI before and after one RLIC treatment, a mean of 4.6 hours apart. The de-identified scans were sent to UCLA where [name] performed CBF analyses and readings blinded to pre- and post-RLIC treatment. After just 1 cycle of RLIC, these subjects showed mean increases of CBF of 8%-28% in the MCA and PCA territories on the infarct side vs. the normal side. While quantitative CBF obtained with ASL MRI is the primary MR outcome in this pilot, we will also utilize dynamic susceptibility contrast enhanced perfusion MR imaging (DSC-PWI) to assess the effectiveness of secondary brain perfusion parameters (such as cerebral blood volume and cerebrovascular transit times).

## **10. ASSESSMENT OF FEASIBILITY, TOLERABILITY AND ADHERENCE TO RLIC**

Enrolled subjects randomized to the RLIC group will take the Doctormate device home and use it daily for the next 30 days. The research coordinator will call the subject weekly up until the close-out visit to document any problems with the device or any adverse events using a questionnaire (see Appendix 1). The subject will also be asked to keep a daily diary for the 30 days the Doctormate device is used (see appendix 2.) The device records when it is used and whether the treatment was completed so when the subject returns for the close-out visit, we will be able to assess adherence to use of the device.

## **11. RANDOMIZATION, BLINDING, AND DATA MANAGEMENT**

Subjects will be randomized 1:1 using a pre-generated exact central randomization list that controls for moderate imbalances at the site level. All study data will be entered directly by either the study PI or stroke coordinator at each site in the RedCap data management system developed at MUSC for the study. Initial data checking will be performed by the system before the data can be saved to prevent low level data errors. When the data are transferred to the study biostatistician for analysis and report generation, further data quality checks will be conducted by SAS. Study data will be retained on a secure server at the Department of Public Health Sciences at MUSC.

## **12. STATISTICAL ANALYSES**

To estimate the variability in CBF and biomarkers, all of which are continuous measures, simple summary statistics will be reported for the baseline and close-out measurements in each group. With five imaging samples per group, the precision of the 90% confidence interval around the mean would be  $\pm 0.95$  for a SD of 1, and, as an example, would increase to  $\pm 7.63$  for a SD of 8. We will also evaluate the changes in CBF and biomarkers from baseline to close-out in the two groups using means and 90% confidence intervals. Here, the precision of the resulting confidence interval is  $\pm 9.4$  when the SD is 8; that is, if RLIC yields a mean 10% change in CBF and sham RLIC yields a mean 0% change in CBF the resulting 90% confidence interval is (0.6, 19.4) for the difference in percent change in CBF. Finally, with a sample size of N=5, we will be able to estimate the correlation between CBF and biomarkers for each arm with an 90% confidence interval of 0.5 (-0.5, 0.9) in the case of an observed moderate correlation. Interpretation of the summary statistics will be complimented with graphical approaches including boxplots to assess distributions within treatment arms, and funnel plots to assess differences at the site level.

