
## 2. PRIMARY AIMS AND LONG-TERM GOAL

As a first step to collect preliminary data on the potential mechanisms of action of RLIC in humans, we will perform a small multicenter randomized pilot clinical trial of 10 subjects with ICAS at 4 participating sites (MUSC, MCG, UCLA and the University of Southern California (USC)) to accomplish the following **primary aims**:

[figure not shown]
- (1) Estimate the variability in CBF (measured by arterial spin labeling and perfusion MRI) and levels of putative biomarkers of the conditioning response (vasodilatory, inflammatory, fibrinolytic, microRNA) in the two treatment groups at enrollment and after 30 days of treatment.
- (2) Compare the changes in CBF and putative blood biomarkers of the conditioning response from enrollment to 30 days between the two treatment groups.
- (3) Obtain preliminary feasibility, tolerability and adherence data on the use of a RLIC device for secondary stroke prevention in subjects with ICAS.

This study will provide preliminary data to enable planning of a subsequent grant submission to NIH to perform a Phase I / II trial with the following goals: to provide more rigorous data on the mechanisms of action of RLIC, and to determine the potential efficacy of RLIC for preventing stroke in high-risk subjects with ICAS. Our ultimate goal is to perform a large randomized multicenter NIH-funded Phase III trial to determine the efficacy of RLIC for preventing stroke.

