### 3. OVERVIEW OF STUDY DESIGN

The design of the study is illustrated in Figure 1 below. In this prospective randomized pilot study, 10 eligible high-risk subjects with ICAS will be randomized to RLIC (bilateral upper extremity (BUE) daily for 30 days) plus AMM (n=5) or AMM alone (n=5). The AMM, which will be started at study enrollment and continued until close-out in all subjects, will consist of aspirin 325 mg per day, clopidogrel 75 mg per day, and risk factor management primarily targeting a systolic BP < 140 mmHg and LDL cholesterol < 70 mg /dl. All subjects will undergo baseline brain arterial spin labeling (ASL) and perfusion MRI to measure CBF and have blood drawn for biomarkers 3-5 days after randomization to allow for washout of any effect from the test RLIC treatment that will be done prior to randomization to determine the subjects' tolerability to RLIC treatment (see section 5 for more details on screening test). The period of 3-5 days will provide flexibility for scheduling these tests. After the baseline MRI and biomarker tests are completed, the subjects randomized to RLIC will begin daily RLIC for 30 days. Each daily BUE RLIC treatment will consist of 4 cycles of 5-minute inflations of both blood pressure cuffs simultaneously to a pressure of 200 mm Hg with 5 minutes of reperfusion between each inflation using the Doctormate device (see Figure 2). All subjects will return for their close-out visits 33-35 days after enrolling in the study and will undergo brain ASL and perfusion MRI and have blood drawn for biomarkers at that visit. The study will be conducted at 4 sites (MUSC, MCG, UCLA, USC) to enable us to evaluate the consistency of CBF measurements across multiple sites and to ensure that the recruitment target of 10 subjects will be met in time to allow for the subsequent NIH grant submission in 2017.

Figure 1. Overview of Study Design

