The principles of Informed Consent, according to FDA Regulations and ICH guidelines on GCP, will be followed. All subjects must provide informed consent to participate and only the participant can provide informed consent, which must be cosigned by a study investigator. Once a subject's eligibility has been confirmed by the site investigators, the subject will be approached to participate in the trial. The consent form includes a section describing a screening process whereby the subject will receive one session of RLIC treatment lasting 5 minutes to ensure that the subject can tolerate the treatment. Subjects who cannot tolerate the treatment will be called by the study coordinator at 1 week but will not participate further in the trial. Only subjects who can tolerate the screening treatment will be randomized to one of the treatment arms.

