**Potential Benefits of the Proposed Research to the Subjects and Others.** Subjects enrolled in this study may benefit from the increased medical supervision that occurs by participating in this study; however, no benefit from this supervision or the RLIC treatment can be guaranteed. If RLIC is indeed effective as suggested in the previous Chinese trials, the subjects randomized to RLIC may have a reduction in stroke. Based on previous human studies, there are minimal risks to RLIC and there is the potential that this treatment could ultimately be shown to be effective for lowering the risk of stroke in patients with ICAS, one of the highest risk stroke-prone conditions.

**Importance of the Knowledge to be Gained.** The risk of recurrent stroke in patients with ICAS is very high, about 20% at one year even with aggressive medical management (AMM). RLIC has the potential to reduce this risk of stroke and avoid disability for patients with ICAS based on the preliminary trials performed in China. Since the anticipated risks of RLIC are low, these risks are reasonable in relation to the importance of the knowledge that will be gained from this study. This study will provide key pilot data to evaluate the tolerability and adherence to RLIC and will enable calculation of the sample size for a subsequent larger NIH-funded

multicenter Phase I / II trial that will provide more rigorous data on the mechanisms of action of RLIC and the potential efficacy of RLIC in preventing stroke in these subjects. If these two goals are achieved in the Phase I / II trial, we will submit another grant to NIH to fund a definitive large multicenter Phase III trial to establish the efficacy of RLIC for subjects with ICAS. If that planned trial is positive for RLIC, it will lead to a new treatment for this common and high-risk disease and will provide a strong rationale to test RLIC for related conditions such as patients with extracranial carotid stenosis and patients with vascular cognitive impairment

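### Section 12 estimates baseline variability only within each arm of 5 and omits the more precise all-subjects estimate that the 10 randomised subjects would support (minor)

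*Combined protocol and SAP*

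**What the plan says.** Section 2 words Aim 1 by group: variability in CBF and biomarkers is to be estimated "in the two treatment groups at enrollment and after 30 days of treatment". Section 12 follows this wording: "simple summary statistics will be reported for the baseline and close-out measurements in each group". Its precision figures for a mean are a 90% half-width of 0.95 for an SD of 1 and 7.63 for an SD of 8, both for five imaging samples per group. It gives no precision for an SD, and no summary over all 10 subjects.

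Other sections describe the state of the two arms at baseline:

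- Section 11: "Subjects will be randomized 1:1 using a pre-generated exact central randomization list".
- Section 13, Risk Analysis and Risk Mitigation: "Only subjects who can tolerate the screening treatment will be randomized to one of the treatment arms". Both arms have therefore had the test inflation.
- Section 3: medical management starts at enrollment in everyone. Subjects have the baseline MRI and "have blood drawn for biomarkers 3-5 days after randomization to allow for washout of any effect from the test RLIC treatment". Then: "After the baseline MRI and biomarker tests are completed, the subjects randomized to RLIC will begin daily RLIC for 30 days".

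Section 13, on the importance of the knowledge to be gained, says that the pilot "will enable calculation of the sample size for a subsequent larger NIH-funded" trial.

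**The concern.** At baseline neither arm has received assigned RLIC. Under randomisation, with the same test inflation and medical management on both sides, the two arms estimate the same baseline mean and the same baseline SD. Splitting by arm gives two estimates of one quantity on 4 degrees of freedom each, where a single estimate on 9 is available.

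This bears on the first listed primary aim, for CBF and the 13 biomarkers in Section 8. If only per-arm values are prespecified, a later planner must choose after the fact between two arm SDs and some pooled version. Two SDs from five subjects each can also look quite different by chance alone.

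**Working it through.** **Inputs.** Ten subjects, 5 per arm (Section 3); 90% two-sided intervals and example SDs of 1 and 8 (Section 12). I assume independent, roughly normal measurements and complete baseline data. Below, s is the observed SD.

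**Step 1: reproduce the plan's figures.** The half-width for a mean is t(0.95, n−1) × SD / √n.

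- n=5: 2.132 × 1 / 2.236 = 0.953; at SD 8, 7.63. Both match Section 12. Normal quantiles would give 0.736 and 5.88, so the plan used t with 4 df.
- Between-arm change at SD 8: t(0.95, 8) × 8 × √(2/5) = 1.860 × 8 × 0.632 = 9.41. This matches the stated 9.4, so the change comparison already draws on all 10 subjects (8 df).

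**Step 2: baseline mean from all 10.**

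- One sample, 9 df: 1.833 × 1 / 3.162 = 0.580; at SD 8, 4.64. The ratio to n=5 is 0.580 / 0.953 = 0.608, or 39% narrower.
- SD pooled within arm, 8 df: 1.860 / 3.162 = 0.588; at SD 8, 4.70.

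**Step 3: baseline SD, the quantity Aim 1 names.** The 90% limits are s × √(df / χ²(0.95, df)) and s × √(df / χ²(0.05, df)).

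| Estimate | df | Lower | Upper | Limits if s = 8 | Upper limit for variance |
|---|---|---|---|---|---|
| One arm | 4 | 0.65 s | 2.37 s | 5.2 to 19.0 | 5.6 s² |
| Pooled within arm | 8 | 0.72 s | 1.71 s | 5.7 to 13.7 | 2.9 s² |
| One sample of 10 | 9 | 0.73 s | 1.65 s | 5.8 to 13.2 | 2.7 s² |

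**Step 4: is anything lost?** With arm means mA and mB, overall mean m, and arm SDs sA and sB, the one-sample SD satisfies

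9 s² = 4 sA² + 4 sB² + 5 (mA − m)² + 5 (mB − m)².

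The per-arm n, mean and SD therefore recover the all-subjects estimate exactly. A numerical check on simulated data gave the same SD by both routes.

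**Step 5: how far apart can two arm SDs fall by chance?** With equal true SDs and normal data, the variance ratio is F(4,4). An SD ratio above 2 in either direction means F > 4 or F < 1/4. Since F/(1+F) then follows a Beta(2,2) distribution, P(F > 4) = 1 − (3 × 0.8² − 2 × 0.8³) = 0.104. Doubling gives 0.21, or about 1 in 5 for each measure.

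**The case against.** Reporting by arm is what Aim 1 asks for. It is also needed to show balance and to read the change scores in Aim 2. That stands, and the fix keeps it.

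A reader might infer that the plan throws away half of the baseline information. The documents do not support this. Sections 8 and 9 plan baseline measurement in all 10 subjects, Section 12 reports both arms, and Step 4 shows that the combined estimate can be rebuilt. What is missing is a named combined estimate, not data.

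A reader might also infer that the next trial's sample size would rest on a variance uncertain by a factor of 5.6 rather than 2.7. That supposes someone would plan from one arm's SD, which nothing in the documents says. Pooling the two arm SDs, an ordinary step, already brings the factor to 2.9. The further gain from one sample is small. Section 13 does not name the baseline SD as the planning input either. A trial powered on change in CBF needs the SD of change, which this point does not touch.

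Finally, equality of the arms at baseline is not quite guaranteed. Measurement comes 3-5 days after assignment, the control is medical management alone, and Section 11 describes no masking of subjects. Different behaviour in those days is possible, though the documents give no reason to expect it to move CBF or biomarkers. Pooling within arm allows for a shift in means and costs one degree of freedom.

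The risk of over-reading two unlike SDs should not be pressed far, since Section 12 plans no between-arm test at baseline.

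**Conclusion.** The point holds as a minor one. Section 12 states baseline estimates and their precision for half of the subjects who could inform them. Against the per-arm estimates as written, the combined estimate narrows the 90% interval for a baseline mean by 39% and lowers the upper limit for the SD from 2.37 s to 1.65 s (1.71 s if pooled within arm). Against an analyst who would pool the two arm SDs anyway, the gain is mainly that the estimate is fixed in advance.

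The conclusion rests on the arms being exchangeable before assigned RLIC starts, on complete baseline data, and, for the SD limits, on approximate normality. It applies to baseline only: close-out follows different treatment in the two arms and cannot be treated as one sample. It does not show that data are wasted or that the next trial's sample size would be wrong.

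**What to change.** Add to Section 12: *The baseline mean and SD of CBF and of each biomarker, with a 90% confidence interval for the SD, will be estimated from all 10 randomised subjects combined (9 df). If the arms are suspected to have diverged after the open assignment, the SD will be pooled within arm instead (8 df). Baseline values by arm will be shown to describe balance.*

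State the baseline precision for a mean as 0.58 × SD (4.64 at SD 8), and keep 0.95 × SD for the close-out summaries, which stay by arm. Because the aim concerns variability, also give the expected 90% limits for an SD: 0.73 s to 1.65 s at baseline, and 0.65 s to 2.37 s for one arm at close-out.

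The cost is a few lines in Section 12 and one extra table column. It needs no new data and no design change.

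### The between-arm comparison uses unadjusted change from baseline; a pre-specified baseline-adjusted estimate beside it would guard against chance imbalance with 5 per arm

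*Combined protocol and SAP*

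**What the plan says.** Primary aim 2 (Section 2) is to "Compare the changes in CBF and putative blood biomarkers of the conditioning response from enrollment to 30 days between the two treatment groups". Section 12 serves this aim by evaluating "changes in CBF and biomarkers from baseline to close-out in the two groups using means and 90% confidence intervals". Its worked example takes a change SD of 8 and a 10-point difference: "the resulting 90% confidence interval is (0.6, 19.4) for the difference in percent change in CBF". The group size is stated as "With five imaging samples per group".

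No analysis of covariance or other baseline adjustment appears anywhere in the document. Section 11 describes the allocation: "Subjects will be randomized 1:1 using a pre-generated exact central randomization list that controls for moderate imbalances at the site level". Baseline CBF and biomarker levels are not balancing factors.

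The covariate is already collected. Section 8 states: "We will measure the blood biomarkers at baseline and close-out (33-35 days after enrollment) in all 10 subjects". Section 9 plans ASL MRI in all 10 subjects at the same two visits. Section 3 places the baseline tests after randomization but before daily RLIC starts, so baseline is unaffected by the 30-day treatment.

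**The concern.** With 5 subjects per arm, the arms can start at visibly different levels of CBF or of a biomarker by chance. Subtracting baseline corrects for this exactly only if the true slope of close-out on baseline is 1. With equal SDs at the two visits that slope is the baseline/close-out correlation, which is below 1. The change score then over-corrects, and the arm that starts lower appears to improve more.

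Aim 2 covers CBF and the 13 biomarkers listed in Section 8, so 14 outcomes. Some of them can be expected to start unbalanced. If the choice between an adjusted and an unadjusted comparison is left until the baseline table has been seen, it becomes data-driven.

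**Working it through.** **1. The plan's own figure.** An unadjusted two-sample t interval with n = 5 per arm and change SD 8 has half-width t(0.95, 8 df) × SD × √(2/5) = 1.860 × 8 × 0.632 = 9.41. Around a difference of 10 this gives (0.59, 19.41), which matches the stated ±9.4 and (0.6, 19.4). The 8 df confirm that no covariate is in the model.

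**2. How often the arms differ at baseline.** The difference in baseline means has SD √(2/5) = 0.632 baseline SDs.
- P(gap > 0.5 SD) = 0.43
- P(gap > 0.63 SD) = 0.32
- P(gap > 1 SD) = 0.11

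Over 14 outcomes, the expected number with a gap above 0.63 SD is 14 × 0.32 ≈ 4.5. This holds however the outcomes are correlated.

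**3. How much carries over.** Write ρ for the baseline/close-out correlation. With equal SDs at the two visits, a baseline gap D moves the expected difference in change by −(1 − ρ) × D. Take SD 8 at each visit. The threshold is then 0.63 × 8 = 5.04 units, and the mean absolute gap in trials beyond it is about 7.70 units (normal distribution, SD 0.632 × 8 = 5.06). The mean shift is (1 − ρ) × 7.70.

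**4. Simulation.** Normal data, 5 v 5, SD 8 at each visit, 200,000 trials per value of ρ. The planned interval uses 8 df. The adjusted one comes from a linear model with arm and baseline (ANCOVA, 7 df). The first four result columns refer to trials with a baseline gap above 0.63 SD.

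| ρ (assumed) | Mean shift, change score | 90% CI coverage, change score | 90% CI coverage, ANCOVA | Root-mean-square error, change score v ANCOVA | Mean CI width over all trials, ANCOVA ÷ change score |
|---|---|---|---|---|---|
| 0.3 | 5.4 | 82% | 90% | 7.4 v 5.7 | 0.88 |
| 0.5 | 3.8 | 85% | 90% | 5.9 v 5.2 | 0.94 |
| 0.7 | 2.3 | 87% | 90% | 4.3 v 4.3 | about 1.00 |
| 0.8 | 1.5 | 88% | 90% | 3.4 v 3.6 | 1.03 |
| 0.9 | 0.8 | 89% | 90% | 2.3 v 2.6 | 1.06 |

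At ρ = 0.2 the width ratio is 0.84. Over all trials, both intervals cover 90% at every ρ. ANCOVA's mean error in the imbalanced trials is about 0. In those same trials its interval is wider than the change-score interval by 4% at ρ = 0.5, 14% at 0.8 and 17% at 0.9.

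**5. Share of the error due to imbalance.** In units of SD² × (2/n), the variance of the change-score difference is 2(1 − ρ), and the part due to the baseline gap is (1 − ρ)². The share is therefore (1 − ρ)/2: 25% at ρ = 0.5, 10% at 0.8 and 5% at 0.9.

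**The case against.** The strongest case for leaving the plan alone is that ANCOVA cannot be shown to be better here. The documents give no correlation. Section 9 keeps each subject on one scanner, which favours a higher value. From about 0.7 upward, adjustment brings no useful gain in error, even in the imbalanced trials, because the slope is estimated from 10 subjects. The pilot plans no hypothesis test, and aim 2 is worded as a comparison of changes. Section 12 also reports baseline and close-out summaries by group, so an imbalance would be visible. All of this stands, and it rules out replacing the planned analysis. It does not argue against reporting an adjusted estimate as well, since the correlation may differ across 14 outcomes and need not be high for all of them.

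Four stronger readings are tempting, and the documents do not support them.
- **The planned estimate is biased, or its interval invalid.** It is neither; the error is conditional on the imbalance observed.
- **The plan implies a correlation of 0.5.** If SD 8 applied both to a single visit and to change, then 8² = 2 × 8² × (1 − ρ) would give ρ = 0.5. But the first SD of 8 is a unit-free illustration beside an SD of 1, and the second is tied to an interval "for the difference in percent change in CBF". They need not share a scale.
- **An apparent RLIC effect could be mostly imbalance.** On average, step 5 shows that most of the error comes from elsewhere.
- **The observed effect goes straight into the next trial's design.** Section 13 says that the pilot will enable a sample-size calculation. It does not say that the observed difference will be the input.

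**Conclusion.** The point holds as a modest refinement. The planned comparison is unadjusted, the baseline values are available, and allocation balances on site only. For each outcome, roughly one trial in three would have a baseline gap above 0.63 SD. In those trials the planned estimate is off in a predictable direction by about 5.4 units at a correlation of 0.3, falling to 0.8 at 0.9, and coverage runs from 82% to 89% instead of 90%.

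These sizes assume normal data, equal SDs of 8 at both visits, a common linear slope and an absolute scale. The plan's example is in percent change, where the relation to baseline differs, so the shifts should not be set directly against its 10-point effect. Because the correlation is unknown, a net gain in precision cannot be claimed. The case rests on correct coverage given the imbalance that occurs, on a cost that is small on average, and on settling the choice before the data are seen.

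**What to change.** In Section 12, pre-specify for CBF and each biomarker a baseline-adjusted between-arm difference in close-out value: a linear model with arm and baseline, a 90% confidence interval on 7 df, on the absolute or log scale. Report it beside the planned change summaries, not in their place. Also report the baseline/close-out correlation for each outcome, which the next trial's sample-size calculation can use.

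The cost is a sentence or two of text, one degree of freedom, and a slope that is imprecise with 10 subjects. The adjusted interval is about 6–16% narrower on average at correlations of 0.2–0.5, breaks even near 0.7, and is 3–6% wider on average at 0.8–0.9 (14–17% in imbalanced trials). No further data collection is needed, and the stated ±9.4 can remain as the precision of the unadjusted summary.
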